8.1 Sample Size Considerations

Both populations, TDT and NTDT have a primary objective of safety, therefore the population sample sizes are not based on statistical assumptions.

8.1.1 Population 1: Transfusion-dependent β-thalassemia

For the secondary efficacy endpoint of percentage of subjects with hematologic improvement (reduction in transfusion burden), 30 subjects in an active treatment arm and 20 subjects in the placebo arm will provide approximately 79% power to detect a difference of 10% of subjects improving in the placebo arm versus 50% of subjects improving in an active treatment arm, using a two-sided alpha level of 0.05. No multiple comparisons adjustments will be made as these are secondary analyses.

8.1.2 Population 2: Non-transfusion-dependent β-thalassemia

For the secondary efficacy endpoints of proportion of subjects with increase from Baseline of ≥ 1.0 g/dL in mean Hb values at Weeks 12 to 24 or Weeks 24 to 36, 30 subjects in an active arm and 15 subjects in the placebo arm will provide approximately 67% power to detect a difference of 10% of subjects improving in the placebo arm versus 50% of subjects improving in an active treatment arm, using a two-sided alpha level of 0.05. No multiple comparisons adjustments will be made as these are secondary analyses.

8.2 Randomization

All subjects who are screened (including screen failures) will be assigned a unique subject identification number.

On Day 1, eligible subjects in Population 1 (TDT Population) and Population 2 (NTDT Population) will be assigned another unique number (randomization number) in sequential order. The randomization number codes the subject's initial treatment assignment according to the randomization schedule generated prior to the study. Initially, subjects will be randomly assigned in a 2:1 ratio to receive either IMR-687 lower dose or placebo. If the DMC recommends inclusion of the higher dose, randomization will then proceed in a 1:2:1 ratio (IMR-687 lower dose, IMR-687 higher dose, or placebo).

Randomization schedules will be generated by Cytel, a subcontractor of the IXRS vendor Suvoda.

Subject randomization will be stratified by TDT/NTDT status.

Randomization number will not be reused once assigned. If a subject discontinues or is discontinued at the discretion of the investigator or DMC up to and including the Week 12 visit, the subject may be replaced with another subject, from the same TDT/NTDT stratum, meeting the eligibility criteria. In the event that a subject is replaced, the replacement subject will receive the same treatment as the replaced subject, and a different leading number will be used for the replacement randomization. Subjects who are replaced, or who are replacement subjects, will be included in the analyses sets according to the same criteria used for all other subjects, as described in Section 11.0.

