### **Independent Data Monitoring Committee Oversight**

This study initially imposed a minimum weight threshold of 45 kg and a 67-kg weight gate for tablet strength to ensure that subjects in the lower dose IMR-687 group received a dose equating to no more than the 4.5 mg/kg evaluated in the MAD part of the healthy volunteer study. Subsequently, the Data Monitoring Committee (DMC) approved the opening of enrollment in the higher dose IMR-687 group (up to 6.7 mg/kg). Having established safety and tolerability of the lower dose, the DMC also approved a change in weight gate to 60 kg and the resultant modified dose range of up to 5.0 mg/kg in the lower dose group (with the minimum weight threshold of 45 kg unchanged). Starting from Protocol Version 5.0, subjects in the IMR-687 lower dose group will receive  $\geq 3.4$  to  $\leq 5.0$  mg/kg and subjects in the higher dose group will receive  $>5.0$  to  $\leq 6.7$  mg/kg; no subject will receive more than 6.7 mg/kg. Under Protocol Version 4.0, the exposure ranges were  $\geq 3.0$  to  $\leq 4.5$  mg/kg in the lower dose group and  $>4.5$  to  $\leq 6.7$  mg/kg in the higher dose group. Therefore, the overall exposure ranges during the course of the study are  $\geq 3.0$  to  $\leq 5.0$  mg/kg and  $>4.5$  to  $\leq 6.7$  mg/kg and are presented as such hereafter.

For this first study evaluating IMR-687 in subjects with  $\beta$ -thalassemia, the DMC has noted some of the related pathology that is shared with patients who have SCD. The shared manifestations include chronic anemia, fatigue, delayed growth, cerebral ischemia, splenomegaly, gallstones, pulmonary hypertension, and leg ulcers. In the phase 2a study in adult subjects with SCD (IMR-SCD-102), IMR-687 has been shown to be well tolerated, with initial evidence of PD effects. The DMC has reviewed interim results from this study and is supportive of the dose exposure and duration of treatment in this first  $\beta$ -thalassemia study.

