8.0 Study Design

This is a phase 2 randomized, double-blind, placebo-controlled study to evaluate the safety, tolerability, PK, and PD of IMR-687 (PDE9 inhibitor) administered QD for 36 weeks in 2 populations of adult subjects with β-thalassemia: Population 1 (TDT subjects) and Population 2 (NTDT subjects). A schematic of the study is provided in Figure 1.

This study will enroll approximately 120 subjects with β-thalassemia (60 subjects with TDT and 60 subject with NTDT), aged 18 through 65 years across approximately 50 sites in North America, the United Kingdom, European Union, Middle East, Asia-Pacific, and Africa. This study consists of a retrospective data collection period, a screening period, a double-blind treatment period, and safety follow-up period. The planned maximum duration of study participation is approximately 44 weeks. During the screening period of up to 28 days, subjects will provide informed consent and be evaluated on eligibility criteria as stated in Sections 8.1 and 8.2 of the study protocol.

Randomization will be stratified by TDT/NTDT status. Subjects will be randomly assigned in a 2:1 ratio to receive either IMR-687 lower dose or placebo. Prior to the introduction of IMR-687 higher dose, the Data Monitoring Committee (DMC) was to review safety data for at least 5 subjects who received IMR-687. If the DMC recommended inclusion of the higher dose, randomization was then to proceed in a 1:2:1 ratio (IMR-687 lower dose, IMR-687 higher dose, or placebo). The DMC could request additional data and/or meeting(s) in order to make the recommendation on whether to move forward with inclusion of the higher dose. During study conduct under Protocol Version 4.0, the DMC approved the opening of enrollment in the higher dose IMR-687 group, which went into effect on 01 February 2021. With approval of enrollment in the higher dose arm, subjects receive IMR-687 lower dose (≥ 3.4 to ≤ 5.0 mg/kg), higher dose [>4.5 to ≤ 6.7 mg/kg] or placebo in a blinded fashion; the precise exposure ranges for different groups of subjects are dependent on the weight gate for tablet strength as summarized below).

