13.0 Statistical Methods

All statistical analyses will be conducted using SAS Version 9.4.

Descriptive summary statistics will be provided for demographics, disposition, and IMR-687 exposure. The number and percentage of subjects who discontinue from the study, along with reasons for discontinuation will be tabulated.

Continuous data will be summarized using descriptive statistics (number of subjects, mean, SD, median, first quartile (Q1), third quartile (Q3), minimum, and maximum, %CV). Frequencies and percentages will be used for summarizing categorical (discrete) data. For summaries of categorical variables, counts and percentages are based on the number of subjects in the analysis set unless otherwise specified.

All statistical tests and resulting p-values will be reported as 2-sided. Confidence intervals, when presented, will be constructed at the two-sided 95% level, unless noted otherwise.

P-values will be presented to 4 decimal places with values less than 0.0001 presented as “<0.0001” and p-values greater than 0.9999 presented as “>0.9999”.

Means, medians, Q1s, and Q3s will be presented to 1 or more decimal places than the recorded data. The SDs will be presented to 2 more decimal places than the recorded data. Confidence intervals about a parameter estimate, minimums, and maximums will be presented using the same number of decimal places as the parameter estimate. Percentages will be presented to 1 decimal place.

A month is operationally defined to be 30.4375 days. A year is defined to be 365.25 days. A week is defined to be 7 days.

Where specified, there will be pair-wise comparisons between IMR-687 lower dose vs. placebo, IMR-687 higher dose vs. placebo and IMR-687 pooled dose vs. placebo.

Separate table and figure outputs will be produced for each TDT/NTDT population. The TDT population may be unblinded and reported at a separate time from the NTDT population depending on enrollment. If this occurs the blind of the unfinished population will be preserved. Listings will include both the TDT and NTDT populations with the TDT population presented first in the listing

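### The higher dose is compared with all placebo patients, including any randomised before it opened, and the SAP plans no concurrent-placebo sensitivity analysis

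*SAP*

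**What the plan says.** SAP 8.2 sets out two allocation schedules. The first is "Initially, subjects will be randomly assigned in a 2:1 ratio to receive either IMR-687 lower dose or placebo". If the DMC agrees, "randomization will then proceed in a 1:2:1 ratio (IMR-687 lower dose, IMR-687 higher dose, or placebo"). SAP 8.0 confirms that the change took place: "the DMC approved the opening of enrollment in the higher dose IMR-687 group, which went into effect on 01 February 2021". Every higher-dose patient therefore entered under the second schedule. A patient who leaves by Week 12 may be replaced, and "the replacement subject will receive the same treatment as the replaced subject".

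SAP 13.0 lists "pair-wise comparisons between IMR-687 lower dose vs. placebo, IMR-687 higher dose vs. placebo and IMR-687 pooled dose vs. placebo". The ITT set is everyone randomised, by assigned arm (SAP 11.2). The per-protocol set has no restriction on randomisation date (11.4), and the table shells have one placebo column (Appendix 6). The SAP never states in words that placebo is pooled over the two schedules, but these provisions leave no other reading.

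TDT/NTDT status is the only randomisation stratum, and the two populations are analysed separately (8.2, 13.6). The CMH tests name no strata and the ANCOVA models adjust for the baseline value (13.6.4.1, 13.6.4.3). The log-rank and Cox analyses name only treatment (13.6.6.3). The sensitivity analyses (13.6.4.4, 13.6.6.4) and subgroups (13.6.4.5) do not include allocation period, and the changes from protocol (6.1) do not raise it.

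**The concern.** A placebo patient randomised at 2:1 had no chance of the higher dose, so randomisation does not make that patient comparable with the higher-dose group. If outcomes differ between periods for reasons other than the drug, the difference enters the higher-dose estimate in proportion to the early share of placebo. As planned, a reader would have no estimate based only on concurrently randomised patients.

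One possible route for a period difference is visible in TDT. Before Protocol Version 5.0, transfusion was not supposed to fall on Day 1; under that version it may follow the last PK sample (SAP Appendix 1, footnote n). SAP 10.1.7 counts a Day 1 transfusion as pre-treatment burden. But Version 5.0 is dated 15 March 2021, not the switch date, and Protocol 9.7.3 still discourages Day 1 transfusion. This shows a possible route, not that drift occurred.

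**Working it through.** **Inputs.** The allocation ratios are from SAP 8.2, the 60 patients per population from SAP 8.0, and 10% v 50% response at two-sided 0.05 from SAP 8.1. The number randomised early (x) and the period difference (D) are not given. x = 12, 24, 36 and null rates moving from 10% to 20% or 30% are assumptions.

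**The plan's own power figures.** SAP 8.1.1 (TDT) uses "30 subjects in an active treatment arm and 20 subjects in the placebo arm" and states about 79%; SAP 8.1.2 (NTDT) uses "30 subjects in an active arm and 15 subjects in the placebo arm" and states about 67%. A continuity-corrected normal approximation reproduces both:
- TDT: z = (0.40 - 0.0417 - 1.96 × 0.1368) / 0.1133 = 0.80, power 78.7%.
- NTDT: z = (0.40 - 0.05 - 1.96 × 0.1524) / 0.1197 = 0.43, power 66.6%.

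**Arm sizes.** With x early and L late patients: higher = L/2; placebo = x/3 + L/4; early share of placebo = (x/3)/(x/3 + L/4); bias = share × D. With x + L = 60:

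| x | Higher | Placebo early + late | Early share | Bias |
|---|---|---|---|---|
| 12 | 24 | 4 + 12 | 25.0% | 0.25D |
| 24 | 18 | 8 + 9 | 47.1% | 0.47D |
| 36 | 12 | 12 + 6 | 66.7% | 0.67D |

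**Type I error.** Exact enumeration of the unstratified, uncorrected CMH test with no drug effect. Early placebo responds at 10%; late placebo and higher dose at the new rate. The value in brackets is for no drift, with everyone at the new rate.

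| x | 10% to 20% | 10% to 30% |
|---|---|---|
| 12 | 4.3% (4.2%) | 5.5% (4.7%) |
| 24 | 6.7% (5.2%) | 9.8% (5.1%) |
| 36 | 8.8% (5.3%) | 13.9% (4.9%) |

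**Precision of a concurrent-only comparison.** Exact CMH power at 10% v 50%, and the ratio of standard errors in a linear model, √[(1/higher + 1/late placebo)/(1/higher + 1/all placebo)]:

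| x | Power, pooled | Power, concurrent | SE ratio |
|---|---|---|---|
| 12 | 80.2% | 70.8% | 1.095 |
| 24 | 78.8% | 52.0% | 1.207 |
| 36 | 69.6% | 35.3% | 1.342 |

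**Do the planning sizes reveal the early share?** Only indirectly.
- NTDT 30 v 15 is exactly what 60 late and no early patients would give, so bias 0.
- TDT 30 v 20 cannot arise from 60 patients with a higher-dose arm: placebo = x/3 + (60 - x)/4 = 15 + x/12, which is 20 only at x = 60.
- If the 30 are higher dose, L = 60 and x/3 + 15 = 20, so x = 15 and the total is 75; 5 of 20 placebo are early.
- If the 30 are lower dose, 2x/3 + L/4 = 30 and x/3 + L/4 = 20, so x = 30, L = 40 and the total is 70; 10 of 20 placebo are early.

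**The case against.** The strongest reply is that no drift has been shown. The error rates above require the null response rate to double or triple between periods, and nothing in the documents says it did. Endpoints compare each patient with their own baseline, treatment is double-blind, and ANCOVA removes drift carried by the baseline value. The documented change in dosing, "the DMC also approved a change in weight gate to 60 kg and the resultant modified dose range of up to 5.0 mg/kg", concerns active tablets that placebo patients do not take. The early count may be small or zero. The objective is safety, and efficacy is secondary or exploratory without multiplicity adjustment (SAP 13.6.1), so no protected error rate is at risk. All of this stands and limits the importance of the point. It does not make the early placebo patients concurrent.

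A second reply is that the extra analysis would rarely reveal drift. With early placebo at 10%, a 10-point drift moves pooled away from concurrent placebo by an expected 2.5/4.7/6.7 points (SD 4.7/8.0/12.3) at x = 12/24/36. A 20-point drift moves it by 5.0/9.4/13.3 points (SD 5.0/8.8/13.7). The signal is about one SD at best. Pooling also has the smaller root mean squared error for drifts below about 35/27/26 points (assuming 50% higher-dose response). This too stands: it is why pooled placebo should remain the lead, and why agreement between the two results must not be read as proof of no drift.

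A third reply concerns the interims. SAP 12.0 suppresses minima, maxima and scatter points because sponsor staff see group results. Pooled and concurrent results side by side would reveal the early placebo patients by subtraction, perhaps only four people. That is decisive against producing the analysis at an interim.

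**Conclusion.** The gap is real but modest. The higher-dose comparison can include non-concurrent placebo, and the SAP offers no concurrent estimate beside it. With 12 of 60 early the inflation is negligible to slight (4.3% v 4.2%, or 5.5% v 4.7%). It is material only when a large early share meets large drift: with 24 to 36 early, 6.7-8.8% v 5.2-5.3%, or 9.8-13.9% v 4.9-5.1%. All of these rest on assumed early counts and drifts.

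A reader might infer more, in two ways. The first is that the higher-dose result is biased or its error rate inflated; that needs an early count and a period difference, and the documents give neither. The second is that the TDT planning sizes show 5 or 10 early placebo patients. Those splits need 75 or 70 patients against about 60 planned, and SAP 8.1 says the sample sizes do not rest on statistical assumptions, so they are not counts.

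**What to change.** Keep pooled placebo as the lead. In SAP 13.6.4.4 and 13.6.6.4, prespecify one sensitivity analysis for the inferential higher-dose v placebo efficacy comparisons, as follows:

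- Use the same method as the lead, with placebo restricted to patients randomised under the 1:2:1 schedule (on or after 01 February 2021).
- Exclude from the concurrent group any post-switch replacement who inherited a pre-switch placebo assignment, since that patient could not have received the higher dose either. The replacement listing already planned in SAP 13.1 identifies them.
- Report early and concurrent placebo counts per population. Where a population has no early placebo patients, say so and omit the analysis.
- Run it at the final analysis only, not at IA 0.5, 1.0 or 2.0.

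A period factor in a three-arm model is not a good substitute. The lower-dose range also changed (Protocol 5.1). If that shifts late lower-dose outcomes by d, the higher-dose estimate shifts by -0.15d, -0.27d or -0.36d at x = 12, 24 or 36.

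The cost is SAP wording and some extra final-analysis tables. The downside is precision: power of about 71/52/35% instead of 80/79/70%, and standard errors about 10/21/34% larger. The result should be presented as a concurrently randomised estimate beside the lead, not as a test for drift.

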9.0 Study Endpoints, Variables and Covariates

Primary Endpoints	TDT	NTDT
IMR-687 safety and tolerability assessed using: 
• Incidence and severity of adverse events and serious adverse events• Incidence of subjects with a post-Baseline clinically significant worsening in the CTCAE laboratory grade for a lab parameter	X	X

 Incidence of subjects with a post-Baseline clinically significant change in a vital signs parameter Incidence of subjects meeting the clinically significant criteria for an electrocardiogram (ECG) parameter Changes from Baseline in 12-lead ECG clinical laboratory test (chemistry, hematology, coagulation, and urinalysis), and vital signs parameters (continuous parameters only) Changes in physical examination findings relative to the Baseline physical examination 		
Secondary Endpoints	TDT	NTDT
Proportion of subjects with a $\geq 20\%$ reduction in RBC transfusion burden with a reduction of at least 2 units of RBCs (hematological improvement) for Week 12 to Week 24 and Week 24 to Week 36, compared to the 12 weeks prior to Baseline (Day 1).	X	
Proportion of subjects with a $\geq 20\%$ reduction in RBC transfusion burden with a reduction of at least 2 units of RBCs (hematological improvement) for Week 12 to Week 36, compared to the 12 weeks prior to Baseline (Day 1).	X	
Proportion of subjects with a $\geq 20\%$ reduction in RBC transfusion burden with a reduction of at least 2 units of RBCs (hematological improvement) for any 12-week rolling time period – Day 2 to 85, Day 3 to 86, etc. through Day 170 to Day 253 (Week 36) – compared to the 12 weeks prior to Baseline (Day 1).	X	
Proportion of subjects with a $\geq 20\%$ reduction in RBC transfusion burden with a reduction of at least 2 units of RBCs (hematological improvement) for any 14-week rolling time period – Day 2 to 99, Day 3 to 100, etc. through Day 156 to Day 253 (Week 36) – compared to the 12 weeks prior to Baseline (Day 1).	X	
Proportion of subjects with a $\geq 33\%$ reduction in RBC transfusion burden with a reduction of at least 2 units of RBCs (hematological improvement) for Week 12 to Week 24 and Week 24 to Week 36, compared to the 12 weeks prior to Baseline (Day 1).	X	
Proportion of subjects with a $\geq 33\%$ reduction in RBC transfusion burden with a reduction of at least 2 units of RBCs (hematological improvement) for Week 12 to Week 36, compared to the 12 weeks prior to Baseline (Day 1).	X	
Proportion of subjects with a $\geq 33\%$ reduction in RBC transfusion burden with a reduction of at least 2 units of RBCs (hematological improvement) for any 12-week rolling time period – Day 2 to 85, Day 3 to 86, etc. through Day 170 to Day 253 (Week 36) – compared to the 12 weeks prior to Baseline (Day 1).	X	
Proportion of subjects with a $\geq 33\%$ reduction in RBC transfusion burden with a reduction of at least 2 units of RBCs (hematological improvement) for any 14-week rolling time period – Day 2 to 99, Day 3 to 100, etc. through Day 156 to Day 253 (Week 36) – compared to the 12 weeks prior to Baseline (Day 1).	X	

Proportion of subjects with a $\geq 50\%$ reduction in RBC transfusion burden with a reduction of at least 2 units of RBCs (hematological improvement) for Week 12 to Week 24 and Week 24 to Week 36, compared to the 12 weeks prior to Baseline (Day 1).	X		
Proportion of subjects with a $\geq 50\%$ reduction in RBC transfusion burden with a reduction of at least 2 units of RBCs (hematological improvement) for Week 12 to Week 36, compared to the 12 weeks prior to Baseline (Day 1).	X		
Proportion of subjects with a $\geq 50\%$ reduction in RBC transfusion burden with a reduction of at least 2 units of RBCs (hematological improvement) for any 12-week rolling time period – Day 2 to 85, Day 3 to 86, etc. through Day 170 to Day 253 (Week 36) – compared to the 12 weeks prior to Baseline (Day 1).	X		
Proportion of subjects with a $\geq 50\%$ reduction in RBC transfusion burden with a reduction of at least 2 units of RBCs (hematological improvement) for any 14-week rolling time period – Day 2 to 99, Day 3 to 100, etc. through Day 156 to Day 253 (Week 36) – compared to the 12 weeks prior to Baseline (Day 1).	X		
Mean number of transfusion events from Baseline to Week 36.	X		
The plasma PK profile of IMR-687 after administration to subjects will be evaluated by determination of PK parameters, as appropriate, for Study Day 1 and Week 3/Week 4 and population PK, based on drug concentration levels in plasma obtained over time.	X	X	
Mean change from Baseline to Week 36 for iron chelation therapy daily dose and serum ferritin.	X	X	
Proportion of subjects with an increase from Baseline of ≥ 1.0 g/dL in mean Hb values at Weeks 12 to 24 and Weeks 24 to 36 in the absence of transfusions.		X	
Mean change from Baseline in mean Hb values at Weeks 12 to 24 and Weeks 24 to 36 in the absence of transfusions.		X	
Mean change from Baseline in mean HbF values at Weeks 12 to 24 and Weeks 24 to 36 in the absence of transfusions.		X	
Proportion of subjects with an increase from Baseline of $\geq 3\%$ in mean HbF values at Weeks 12 to 24 and Weeks 24 to 36 in the absence of transfusions.		X	
Exploratory Endpoints		TDT	NTDT
The PD effects of IMR-687 from Baseline to Week 36, as measured by the mean change from Baseline in serum PD markers of erythropoiesis, iron metabolism, and hemolysis.	X	X	
Mean change in transfusion burden expressed as units of RBCs as a continuous variable during Week 12 to Week 24, Week 24 to Week 36, and Week 12 to Week 36, compared to the 12 weeks prior to Baseline (Day 1).	X		

The proportion of subjects who are transfusion independent for ≥ 8 weeks during treatment.	X	
Mean change from Baseline in TranQOL quality of life tool at Weeks 12, 24, and 36.	X	
Mean change from Baseline in SF-36 quality of life tool at Weeks 12, 24, and 36.	X	X
Pharmacogenomic analyses of genes that may affect treatment response (including α -globin, gamma-globin Xmn1 polymorphism, and BCL11A).	X	X
Proportion of subjects who have an Hb increase of ≥ 1.0 g/dL from Baseline for ≥ 14 days in the absence of RBC transfusions.		X
Proportion of subjects who are RBC transfusion-free over 36 weeks and other variables of transfusion burden.		X
Duration of the mean Hb increase from Baseline of ≥ 1.0 g/dL over 36 weeks.		X
Proportion of subjects who have an increase from Baseline ≥ 1.5 g/dL in mean of Hb values at Week 24 and Week 36 compared to Baseline in the absence of transfusions.		X
Mean number of transfusion events from Baseline to Week 24.	X	
Mean change from Baseline in NTDT-PRO tiredness/weakness (T/W) domain score over a continuous 12-week interval from Week 12 to Week 24 and Week 24 to Week 36.		X
Mean change from Baseline in NTDT-PRO total score and T/W domain score at Week 24 and Week 36.		X
Mean change in biomarkers from Baseline to Week 36, stratified by genotype. ^a	X	X
Time to first Hb increase (≥ 1.0 g/dL)		X

ECG = electrocardiogram; Hb = hemoglobin; HbF = fetal hemoglobin; LDH = lactate dehydrogenase; NTDT = non-transfusion dependent β -thalassemia; NTDT-PRO = non-transfusion dependent β -thalassemia patient reported outcome; PD = pharmacodynamics; PK = pharmacokinetics; pRBC = packed red blood cells; PRO = patient-reported outcome; RBC = red blood cell; SF-36 = Short Form (36) Health Survey; t_{max} = time to maximum plasma concentration; TDT = transfusion dependent β -thalassemia; TranQOL = transfusion-dependent quality of life.

^a See Section 13.6.8 for list of biomarkers.

